Biomarkers predictive of clinical efficacy and toxicity are emerging for VEGF directed therapies. In a recent randomized placebo-controlled phase III study (ECOG 2100) of paclitaxel plus bevacizumab (a recombinant humanized monoclonal antibody to VEGF) in the first-line treatment of metastatic breast cancer, patients who received bevacizumab demonstrated a significant prolongation of progression free survival (11.8 vs. 5.9 months, HR=0.60 p=0.001) (Miller et al., 2007). When the entire study population was analyzed (n=772), no significant differences in median overall survival were observed between patients who received bevacizumab and those who received placebo (26.7 months vs. 25.2 months, HR 0.88 p=0.15). In a planned biomarker analysis, the breast cancer tumor genotype frequencies of single nucleotide polymorphisms (SNPs) in seven VEGF and VEGF receptor genes were determined from patient formalin fixed paraffin embedded tissue blocks (FFPE). Patients whose tumors possessed a VEGF (-2578 AA) or a VEGF (-1154 AA) genotype had a marked statistically significant improvement in median overall survival in association with bevacizumab therapy (-2578 AA genotype HR 0.58 p=0.023, -1154 AA genotype HR 0.62 p=0.001) (Schneider et al., 2008). Furthermore, significant associations between hypertension and patients with the VEGF (-634 CC) genotype (p=0.005) and the VEGF (-1498 TT) genotype (p=0.022) were also observed. Confirmation of these observations is planned in a prospective large randomized phase III trial testing the role of bevacizumab in addition to standard chemotherapy for breast cancer patients in the adjuvant setting. Lastly, investigators have also observed associations between the development of treatment related hypertension and favorable clinical outcomes in patients treated with VEGF directed therapies (Bono et al., 2011). To date, no predictors of response to VEGF directed therapy have been examined or reported in bladder cancer. Therefore as additional secondary objectives of this trial we plan to assess associations between improved biologic and clinical outcomes according to VEGFR over-expression, host VEGFR mutation, and treatment related hypertension status.

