### 3.3.1 Endpoint for Exploratory Objectives

- Presence of FGFR3 mutations (see Table 1-2) in tumor tissue and urine will be assessed by massively parallel sequencing of exons 7, 10, and 15 utilizing the Ion Torrent PGM instrument. Presence of FGFR3 mutations within patient free plasma will be assessed by PCR-amplification of the target regions and sequencing.
- Pre-treatment germline FGFR SNPs will be assessed by testing extracted DNA from patient PBMC's (collected prior to initiating dovitinib therapy) with validated commercial probes.
- Pre-treatment germline VEGFR SNPs will be assessed by testing extracted DNA from patient PBMC's (collected prior to initiating dovitinib therapy) with validated commercial probes.
- Presence of VEGFR over-expression within tumor tissue will be assessed and interpreted by standard immunohistochemistry analysis with appropriate controls.
- Pre- and post-treatment bladder tumor FGFR and VEGFR pathway phosphorylation changes will be assessed by bladder tumor tissue immunohistochemistry utilizing commercially available antibodies including, but not limited to, the following: FGFR3, pFGFR3, VEGFR2, pVEGFR2, FRS2, pFRS2, ERK, pERK.
- Post-treatment bladder tissue dovitinib concentrations will be assessed by TURBT fresh frozen tissue obtained at the 3-month cystoscopy
- Hypertension will be defined as a systolic blood pressure (SBP) of  $\geq 140$  mmHg or a diastolic blood pressure (DBP) of  $\geq 90$  mm Hg recorded at any time after dovitinib therapy is initiated.

Objectives and related endpoints are described in [Table 3-1](#) below.

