**Figure 4-1 Study design**

#### 4.1.1 Investigational Treatment, Other Study Treatment, Study Treatment, Supportive Treatment

Investigational treatment in all patients will consist of oral dovitinib 500 mg taken once daily for 5 consecutive days followed by 2 days off repeated every week. Each treatment cycle will be defined as 28 days (4 weeks). In patients not experiencing significant toxicity or relapsed disease, a study-defined maximum number of dovitinib cycles will not be stipulated. Dovitinib will be supplied in the form of 100 mg hard gelatin capsules or film coated tablets.

Standard of care cystoscopy and urine cytology will be performed every 3 months  $\pm$  7 days during the first 12 months of follow-up and per the treating urologist's discretion thereafter. Standard of care tumor biopsy and bladder biopsies will be performed every 3 months  $\pm$  7 days during the first 6 months of follow-up and per the treating urologist's discretion thereafter.

Anti-emetic medications are permitted at the discretion of the treating physician.

Colony stimulating growth factor (i.e. erythropoietin, darbopoeitin, pegfilgrastim, etc.) support is permitted at the discretion of the treating physician.

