## 7.6 Treatment Period

All patients will be treated until either: 1) relapsed disease is noted; 2) Treatment related toxicity requiring a third dose reduction is encountered; 3) Treatment related toxicity not yet requiring a third dose reduction but per the treating physician's discretion is deemed unsuitable for further dovitinib therapy is encountered; or 4) Patient electively foregoes further dovitinib therapy at any time.

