### **7.10.12 Efficacy**

#### **7.10.12.1 6-month Complete Response Rate (6-month CR rate)**

The 6-month complete response (CR) rate is defined as the proportion of patients treated with dovitinib with no evidence of any remaining urothelial carcinoma tumors of any T-stage (including Tis) present within the bladder as assessed by standard of care cystoscopic examination with TURBT and urine cytology performed at 6 months after initiation of study therapy.

**NOTE:** Patients with residual non-invasive UC tumors with no component of carcinoma in situ (i.e. Ta, T1) at 3-month cystoscopy and TURBT are not considered relapses and will be permitted to continue on dovitinib therapy. If the subsequent 6-month cystoscopy, TURBT, and urine cytology shows no evidence of any remaining urothelial carcinoma in such patients, they will be considered a complete response. Patients with any component of carcinoma in situ (CIS) at 3-month cystoscopy/TURBT will be considered relapses and will not continue on dovitinib therapy. Any non-invasive UC tumors (i.e. Ta, T1, Tis) at the 6-month or any subsequent cystoscopy/TURBT is considered relapsed disease. Similarly progression to invasive UC tumors (T2-T4) at any time point is also considered relapsed disease and patients will not continue on dovitinib therapy.

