#### **10.7.1 Exploratory Objectives Statistical Hypothesis, Model, and Method of Analysis**

All exploratory objectives are hypothesis generating in nature. Pre- and post-treatment phosphorylation changes in FGFR and VEGFR pathways will be analyzed by paired t-tests. FGFR SNPs, VEGFR SNPs, post-treatment hypertension, and baseline clinical factors of interest (e.g. age, ECOG PS, Charlson Comorbidity Index, gender, T1 vs. CIS, number of prior intravesical therapies, etc.) will be analyzed by univariate logistic regression and Cox regression for significant associations with 6-month CR and 1-year RFS rates, respectively. No multivariate models will be adopted given the small sample size. Concordance rates between tumor, urine, and circulating free plasma FGFR3 mutations will be summarized by Goodman-Kruskal gamma. The post-treatment bladder tissue dovitinib concentrations will be summarized by mean, standard deviation, minimum, median, maximum, and boxplot. Transformations to normality will be considered when necessary.

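### Exploratory analyses: blood pressure readings taken after complete response is decided count as hypertension exposure, and Goodman-Kruskal gamma does not measure concordance

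*Combined protocol and SAP*

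**What the plan says.** **Hypertension.** Section 3.3.1 defines it as systolic pressure of at least 140 mmHg or diastolic of at least 90 mmHg "recorded at any time after dovitinib therapy is initiated". It gives no end date and does not require new onset. Section 10.7.1 lists it in one group, "FGFR SNPs, VEGFR SNPs, post-treatment hypertension, and baseline clinical factors of interest", which "will be analyzed by univariate logistic regression and Cox regression for significant associations with 6-month CR and 1-year RFS rates, respectively". No exposure window, landmark or time-dependent coding is stated.

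**Who keeps having readings.** Section 7.6: "All patients will be treated until either: 1) relapsed disease is noted". For patients without relapse or significant toxicity, Section 4.1.1 says "a study-defined maximum number of dovitinib cycles will not be stipulated". Section 7.10.12.1 adds: "Any non-invasive UC tumors (i.e. Ta, T1, Tis) at the 6-month or any subsequent cystoscopy/TURBT is considered relapsed disease". CIS at month 3 is also relapse and stops treatment. Section 7.10.4 takes vital signs at baseline and at later study visits.

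**Rationale.** Section 1.2.3 reports from other studies "associations between the development of treatment related hypertension and favorable clinical outcomes". That section calls the hypertension question secondary, whereas Sections 3.3 and 10.7 list it as exploratory. It is treated as exploratory here.

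**Concordance.** Section 10.7.1: "Concordance rates between tumor, urine, and circulating free plasma FGFR3 mutations will be summarized by Goodman-Kruskal gamma". No agreement statistic is named anywhere.

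**The concern.** CR is settled at month 6, but exposure can be acquired afterwards. A patient with tumour at month 6 normally leaves treatment and its cycle visits, while a patient in CR goes on being measured. The responder therefore has more chances to be labelled hypertensive, some of them after the outcome is known. In the Cox model the same mechanism is immortal-time bias: a patient must stay relapse-free to reach the later readings. The artefact points the same way as the association cited in Section 1.2.3, so a spurious result could pass for confirmation.

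Baseline pressure raises a second problem. Section 5.2 excludes only from 160/100, so a patient who enters between 140/90 and that limit could later count as having post-treatment hypertension without any change.

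For the mutation assays, the objective asks how often specimens agree. Gamma answers a different question and can rank a worse-agreeing assay above a better one.

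**Working it through.** The plan gives no figure to reproduce for either part.

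**(a) Hypertension**

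*Readings, from the visit days in Table 7-1, with cycle 1 day 1 taken as pre-dose.* Days 12, 26, 40 and 54, then 82, 110 and so on every 28 days to 362. That gives 5 readings by month 3, 8 by month 6, 11 by month 9 and 15 by month 12. Seven of the 15 fall after CR is decided.

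*Assumptions.* Only the 25% CR rate comes from the plan (Section 10.8). Assumed relapse is 0.35 at month 3 and 0.615 of the remainder at month 6 (0.65 × 0.615 = 0.40, leaving 0.25 in CR), then 0.25 at month 9 and 0.15 at month 12. The chance q of a qualifying reading is 5, 10 or 15% and unrelated to outcome. It varies between patients as a beta distribution with within-patient correlation ρ.

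*Formula.* For independent readings, P(ever) = 1 − (1 − q)^k after k readings. For ρ > 0, P(ever) = 1 − Π (b + i)/(a + b + i) over i = 0 to k − 1, with a = q(1/ρ − 1) and b = (1 − q)(1/ρ − 1). Non-CR patients mix k = 5 (weight 0.35) and k = 8 (weight 0.40). CR patients mix k = 11 (0.25) and k = 15 (0.75).

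*Example, q = 10%, ρ = 0.2.* P(ever) is 0.482 in CR and 0.351 in non-CR. The odds ratio is (0.482/0.518)/(0.351/0.649), or 1.73 unrounded. One extra final-visit reading for patients relapsing before month 12 gives 0.486 and 0.376, odds ratio 1.57.

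Spurious CR odds ratio at q = 5/10/15%:

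| ρ | Relapsers have a final-visit reading | They do not |
|---|---|---|
| 0.2 | 1.49 / 1.57 / 1.67 | 1.62 / 1.73 / 1.85 |
| 0.4 | 1.30 / 1.33 / 1.37 | 1.38 / 1.42 / 1.46 |
| 0 (near worst case) | 2.27 / 2.87 / 3.80 | 2.61 / 3.36 / 4.53 |

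Without the final-visit reading, the simulated Cox hazard ratio for relapse is 0.77/0.75/0.72 at ρ = 0.2 and 0.84/0.82/0.82 at ρ = 0.4.

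*Against the precision available.* With 5 CR and 15 non-CR patients, q = 10% and ρ = 0.2, the standard error of the log odds ratio is √[1/(5 × 0.482) + 1/(5 × 0.518) + 1/(15 × 0.351) + 1/(15 × 0.649)] = 1.05. The bias is ln 1.73 = 0.55, about half a standard error. Simulated false-positive rates for a two-sided 5% score test at n = 20, without the final-visit reading, are about 6 to 9% at ρ = 0.2 and 5 to 6% at ρ = 0.4.

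*Which cut-off removes it.* Counting only readings to month 6 leaves 1.15/1.17/1.20 at ρ = 0.2, because month-3 relapsers stop after 5 readings. A landmark at cycle 2 day 26 (day 54), when everyone still on treatment has had 4 scheduled readings, gives odds ratios of 0.99 to 1.02 and hazard ratios of 0.99 to 1.01.

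**(b) Gamma**

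For a 2×2 table with cells a (both positive), b (tumour only), c (urine or plasma only) and d (both negative), gamma = (ad − bc)/(ad + bc). If b or c is zero and a and d are not, gamma is 1 whatever the size of the other discordant cell.

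| a, b, c, d | Gamma | Agreement (a + d)/20 | Kappa |
|---|---|---|---|
| 3, 7, 0, 10 | 30/30 = 1.00 | 65% | 0.30 |
| 9, 1, 0, 10 | 90/90 = 1.00 | 95% | 0.90 |
| 9, 1, 1, 9 | 80/82 = 0.98 | 90% | 0.80 |
| 8, 2, 2, 8 | 60/68 = 0.88 | 80% | 0.60 |

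The 65% table outranks both the 90% and the 80% table.

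**The case against.** A reader might infer that readings after month 6 come only from responders. The documents do not support that. Section 10.1 classes a patient without a 6-month evaluation as non-CR, yet a missed evaluation is not a stopping reason in Section 7.6, so such a patient may stay on drug and be measured. Section 7.7 requires final-visit assessments after discontinuation, and unscheduled readings also count. Non-relapsers who stop the drug early lose the cycle visits: if 30% stop by month 6, the odds ratios at ρ = 0.2 without a final-visit reading fall to 1.46/1.51/1.55. The pattern is almost only responders.

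A reader might also take the independent-reading row, with odds ratios up to 4.5, as the expected size. Independent readings within one patient are implausible, and that row is a sensitivity case. The end-of-treatment entry for vital signs in Table 7-1 could not be read reliably in the text available, so both versions are shown.

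Fixed coding is inferred. Section 10.7.1 does not rule out a time-dependent covariate in the Cox model, so the fault is a missing specification rather than a stated wrong method. Listing hypertension with baseline factors makes the inference reasonable, and no such coding would rescue the logistic model for CR.

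On baseline pressure, the vital-signs shift table in Section 10.6.3.4 will show pre-existing elevation descriptively. It does not change the regression covariate. On concordance, the frequencies and percentages promised in Section 10.1 help in part, but gamma remains the only summary named for this objective.

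**Conclusion.** Both parts hold, at the level of hypothesis-generating analyses.

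(a) As written, the hypertension analysis can shift the estimate towards a favourable association when there is none. The spurious CR odds ratio is about 1.5 to 1.7 at within-patient correlation 0.2 and 1.3 to 1.4 at 0.4 if relapsers have a final-visit reading, or 1.6 to 1.9 and 1.4 to 1.5 if not. These sizes rest on assumed reading probabilities, correlation and relapse split, none of which the documents give. If every onset comes before month 3, there is no bias. A reader might infer a large excess of false positives, but with correlated readings the rate stays near nominal and the shift is well under one standard error.

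(b) That gamma does not measure agreement is algebraic and needs no assumption.

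Neither part supports any inference about the primary CR estimate, the sample size or the early stopping rule.

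**What to change.** **Hypertension.** In Section 10.7.1, define new-onset hypertension as baseline below 140/90 followed by a reading at or above it, by a landmark before the 3-month cystoscopy, for example cycle 2 day 26. Analyse CR and RFS in patients still at risk at that point. A time-dependent covariate is an alternative for the Cox model only; keep the landmark for CR. Report patients with baseline pressure of 140/90 or above separately. Reconcile the secondary label in Section 1.2.3 with the exploratory label in Sections 3.3 and 10.7.

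**Concordance.** Replace gamma with positive, negative and overall percent agreement with confidence intervals for each specimen pair, taking tumour as the reference where it is one of the pair. Give kappa only as a supplement. If every tumour is mutation-positive, negative agreement is undefined and kappa uninformative, so report positive agreement only.

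**Cost.** Wording only; the readings and assay results are already collected. Later-onset cases no longer count: at ρ = 0.2 the exposed share falls from about 21/38/52% to 14/27/38%, so precision drops. Patients who leave before the landmark do not contribute. The agreement intervals will be wide: the 90% Agresti-Coull interval is 12 to 56% for 3/10 and 64 to 99% for 9/10.

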### 3.2.1 Endpoint for Secondary Objectives

- The 1-year relapse free survival rate is defined as the proportion of patients treated with dovitinib with no evidence of any remaining urothelial carcinoma tumors at 12 months of follow-up.

**NOTE:** Patients with residual non-invasive UC tumors with no component of carcinoma in situ (i.e. Ta, T1) at 3-month cystoscopy and TURBT are not considered relapses and will be permitted to continue on dovitinib therapy. If the subsequent 6-month cystoscopy/TURBT, and urine cytology shows no evidence of any remaining urothelial carcinoma in such patients, they will be considered a complete response. Patients with any component of carcinoma in-situ (CIS) at 3-month cystoscopy/TURBT will be considered relapses and will not continue on dovitinib therapy. Any non-invasive UC tumors (i.e. Ta, T1, Tis) at the 6-month or any subsequent cystoscopy/TURBT is considered relapsed disease. Similarly progression to invasive UC tumors (T2-T4) at any time point is also considered relapsed disease and patients will not continue on dovitinib therapy.

- The rate of progression to muscle-invasive stage for dovitinib is defined as the proportion of patients with clinical or pathologic progression to muscle-invasive stages (i.e. T2-T4) at any time point on study. Pathologic progression is assessed by histological finding at TURBT or cystectomy. Clinical progression is assessed by clinician's physical exam and findings on radiologic imaging as ordered per the treating physician's discretion.
- The 3- and 6-month partial response rates are defined as the proportion of patients treated with persistent but reduced T-stage tumors on post-therapy TURBT (i.e. T1 -> Ta; T1+Tis -> T1).
- Treatment related toxicity rates will be assessed by CTCAE v4.0.

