#### **7.10.12.2 Relapse Free Survival (RFS)**

Relapse Free Survival (RFS) is defined as the time from study registration until the occurrence of any of the following relapse events:

1. Evidence of any component of CIS at 3-month cystoscopy/TURBT
2. Recurrent tumor  $\geq$  T2 at any time point
3. Recurrent tumor of any stage that occurs at or after the 6-month cystoscopy evaluation as assessed by bladder cystoscopy, TURBT, or urine cytology. Note: While not required as part of the study follow-up testing, positive urine FISH test (even if an isolated finding) at or after the 6-month study evaluations will be considered relapsed disease.
4. Documentation of metastatic urothelial carcinoma at any time point

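### Because the RFS definition counts non-muscle-invasive tumor at 3 months only when it contains CIS, the planned Cox regression of RFS on T1 versus CIS is biased against CIS when 3-month histology tracks baseline histology

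*Combined protocol and SAP*

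**What the plan says.** Section 7.10.12.2 makes RFS a time-to-event variable: "Relapse Free Survival (RFS) is defined as the time from study registration until the occurrence of any of the following relapse events". The list has four items. The first is "Evidence of any component of CIS at 3-month cystoscopy/TURBT". The second is recurrent tumor of T2 or above at any time. The third is "Recurrent tumor of any stage that occurs at or after the 6-month cystoscopy evaluation". The fourth is "Documentation of metastatic urothelial carcinoma at any time point".

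The note in Section 3.2.1, repeated in 3.1.1, 7.10.7.1 and 7.10.12.1, gives the other half of the 3-month rule: "Patients with residual non-invasive UC tumors with no component of carcinoma in situ (i.e. Ta, T1) at 3-month cystoscopy and TURBT are not considered relapses". Such patients continue dovitinib and can still be complete responders at 6 months. Patients with any CIS at 3 months are relapses and stop dovitinib. Section 7.10.12.3 builds the 1-year RFS proportion on the relapse definitions.

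Section 10.7.1 then plans univariate models for SNPs, hypertension and baseline clinical factors, including "T1 vs. CIS, number of prior intravesical therapies, etc.) will be analyzed by univariate logistic regression and Cox regression", with Cox regression used for RFS. It adds that "All exploratory objectives are hypothesis generating in nature" and that "No multivariate models will be adopted given the small sample size". It gives no landmark and no alternative event time for the stage comparison.

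**The concern.** The stage covariate and the 3-month event rule both depend on CIS. A patient who enters with CIS and still has CIS at 3 months has an event at 3 months. A patient who enters with T1 and still has T1 at 3 months has no event then, and may never have one. If residual tumor tends to keep its baseline histology, part of any hazard ratio for CIS comes from the definition and not from how the tumors behaved.

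What is at stake is interpretation. A raised hazard ratio for CIS could be read as a prognostic difference or as lower sensitivity to dovitinib, and could shape the choice of population for a later study. More patients would not cure it: a larger sample would estimate the same artefact more precisely.

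**Working it through.** The documents give no figure for this regression, so there is none to reproduce. The check applies the 7.10.12.2 rules to two groups with the same tumor process.

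**Two patient records under the rule**

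- Baseline T1; T1 at 3 months; clear at 6, 9 and 12 months: no event by 12 months.
- Baseline CIS; CIS at 3 months: event at 3 months, whatever follows.

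**Inputs**

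- From the documents: cystoscopy at 3, 6, 9 and 12 months (7.10.7.1) and the event list (7.10.12.2).
- Assumed, identical in both groups: probability p of tumor at 3 months, 0.4 or 0.6; probability s that such tumor is still present at 6 months, 0.5, 0.7 or 0.9; recurrence probability r = 0.2 at each later visit when clear.
- Assumed, and decisive: c, the probability that a 3-month residual contains CIS. Full persistence means c = 0 for baseline T1 and c = 1 for baseline CIS. Weaker tracking is taken as 0.2 and 0.8.
- T2 or above and metastatic disease are left out because the rule treats them alike in both groups.

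**1-year RFS in closed form**

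RFS = (1 − p)(1 − r)³ + p(1 − c)(1 − s)(1 − r)²

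With full persistence, the second term is zero for CIS. For p = 0.6 and s = 0.5:

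- CIS: 0.4 × 0.8³ = 0.205
- T1: 0.205 + 0.6 × 0.5 × 0.8² = 0.205 + 0.192 = 0.397

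| p | s | T1 | CIS |
|---|---|---|---|
| 0.4 | 0.5 | 0.435 | 0.307 |
| 0.4 | 0.7 | 0.384 | 0.307 |
| 0.4 | 0.9 | 0.333 | 0.307 |
| 0.6 | 0.5 | 0.397 | 0.205 |
| 0.6 | 0.7 | 0.320 | 0.205 |
| 0.6 | 0.9 | 0.243 | 0.205 |

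With 0.2/0.8 tracking, p = 0.6 and s = 0.5:

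- T1: 0.205 + 0.6 × 0.8 × 0.5 × 0.64 = 0.358
- CIS: 0.205 + 0.6 × 0.2 × 0.5 × 0.64 = 0.243

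**Hazard ratio, CIS versus T1 (large-sample simulation, Efron ties)**

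- Full persistence: about 1.3 to 1.7 at p = 0.4 and about 1.7 to 2.5 at p = 0.6.
- 0.2/0.8 tracking: about 1.2 to 1.7 over the same scenarios.
- 3-month CIS unrelated to baseline stage (0.5/0.5): 1.0.

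A second set of assumptions (p from 0.40 to 0.75, clearance by 6 months from 0 to 0.33, r = 0.15) gives 1.23 to 2.83 with full persistence. When no residual clears and p = 0.60, the 1-year rates are equal (0.25 and 0.24), yet the hazard ratio is 1.53. In that case the excess comes only from dating CIS events 3 months earlier.

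**Small-sample error**

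With an assumed 10 versus 10 patients, the nominal 5% test rejects in about 10 to 39% of trials under full persistence and about 5 to 17% under 0.2/0.8 tracking.

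**Check of the remedy**

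In the second set, with p = 0.60 and 20% cleared by 6 months, the protocol rule gives a hazard ratio of 1.83 and 28% rejection. If any tumor at 3 months counts in both groups, the same inputs give 1.00, 1-year RFS of 0.246 in each group, and 5.4% rejection.

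**The case against.** The strongest reply is that the asymmetry is deliberate. The protocol states several times that CIS at 3 months is a relapse that ends treatment while residual Ta or T1 is not, so a regression on protocol RFS correctly describes relapse as the protocol defines it. That stands. What is unsafe is reading the coefficient as a difference in tumor behavior, and Section 10.7.1 gives no warning against it.

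Second, histology can change. Section 7.10.12.5 lists Tis to Ta and T1 + Tis to T1 as partial responses. This stands too: such changes dilute the bias, and the full-persistence figures are an upper case. The bias vanishes only if CIS at 3 months is unrelated to baseline stage.

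Third, the 10-versus-10 split has no support in the documents. Section 7.5 records five stage groups, Ta-only patients fall outside the contrast, and nothing says where T1 + Tis and Ta + Tis go. The rejection rates are therefore illustrative.

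Fourth, the analysis is exploratory, and tumor stage is not among the objectives in Section 3.3. That limits the importance of the point. But a hypothesis-generating label excuses imprecision, not an association that the definition itself produces.

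**Conclusion.** The concern holds in expectation and conditionally: the T1-versus-CIS hazard ratio for RFS is biased against CIS whenever 3-month residual histology follows baseline histology. The sizes rest on assumed rates of tumor presence, persistence and recurrence and, above all, on the assumed degree of tracking.

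It touches one of the six example clinical factors in Section 10.7.1, or one of nine named factors once FGFR SNPs, VEGFR SNPs and hypertension are included. The primary endpoint and the descriptive 1-year RFS rate are untouched.

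A reader might infer more than the documents support:

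- That nothing but CIS counts at 3 months. T2 or above and metastatic disease also count, equally in both groups, so they do not remove the bias.
- That the regression must show worse RFS for CIS, or that any such finding is wholly spurious. A single trial of about 20 patients need not show it, and a real difference could exist alongside the artefact.
- That the RFS definition or the rule for continuing treatment is itself in error. The inconsistency lies in using this outcome with this covariate.

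**What to change.** Add to Section 10.7.1:

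1. T1 versus CIS, and any other stage factor based on CIS, is analysed against a stage-neutral event time: tumor of any stage at the 3-month or any later evaluation is an event, among patients with a 3-month evaluation.
2. A statement of how T1 + Tis and Ta + Tis are classed in the comparison.
3. Any stage comparison on protocol RFS is reported with the caveat that part of the difference comes from the event definition.

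Protocol RFS and the treatment-continuation rules stay as they are. The restriction in item 1 is needed because Section 7.8 foresees withdrawal before the first post-therapy TURBT, so not every patient will have that evaluation.

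A 6-month landmark is an alternative, but by then patients with CIS at 3 months have stopped dovitinib and those with residual Ta or T1 have continued, so later events would mix stage with treatment.

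The cost is a few sentences and one derived variable from data already scheduled. The drawbacks are two event-time definitions in the exploratory section and an awkward case: a patient with residual Ta or T1 at 3 months who clears by month 6 is an event in this one analysis but a complete response for the primary endpoint. The text should say so.

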#### **7.10.6.2 FGFR3 Overexpression Status**

Presence of FGFR3 over-expression within tumor tissue will be assessed at study entry by the IUSCC's IHC Core. The IHC antibody used to determine FGFR3 over-expression is commercially available from Novus Biologicals.

Refer to SPM for collection, labeling and shipping guidelines.

Presence of FGFR3 over-expression within tumor tissue will be assessed and interpreted by two separate pathologists. Brain, kidney, and testes are the recommended positive controls. Non specific immune serum will be used as the negative control. Staining intensity will be graded 0, +1, +2, +3 and  $\geq +1$  brown staining in the tissues defines positivity. Up to 3 pieces of tissue are to be analyzed at 3 to 5 high power fields if available.

Upon completion of testing, the presence/absence of FGFR3 over-expression will be communicated to the treating site within 5-7 days.

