#### **10.8 Sample Size Calculation**

The 6-month CR rate will be estimated with a one-sided 90% confidence interval of Agresti-Coull type with the lower bound to be calculated and the upper bound set as 1. With an expected CR rate of  $\geq 25\%$ , a sample size of 20 patients will have a power of 0.80 to exclude a lower bound being  $\leq 10\%$ .

Using a conservative estimate of FGFR3 mutation or over-expression present in 40% of BCG-refractory tumors, 50 patients will need to be screened in order to enroll the required 20 patients on dovitinib therapy.

The estimated accrual duration is 12 months and the estimated overall study duration is 2 years.

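### Section 10.7.1 plans ordinary logistic regression for 6-month CR with about 5 CRs expected and no provision for empty cells, which will be frequent for uncommon categorical factors

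*Combined protocol and SAP*

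**What the plan says.** Section 10.7.1 lists the candidate predictors as "FGFR SNPs, VEGFR SNPs, post-treatment hypertension, and baseline clinical factors of interest", the last group including age, performance status, comorbidity index, gender, T1 versus CIS and number of prior intravesical therapies. These "will be analyzed by univariate logistic regression and Cox regression for significant associations with 6-month CR and 1-year RFS rates, respectively". The section bars multivariable models because the sample is small. It names no exact or penalised method, no test statistic (Wald, score or likelihood ratio) and no coding for genotypes. It describes all these analyses as hypothesis generating.

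The number of responders follows from section 10.8: "a sample size of 20 patients will have a power of 0.80 to exclude a lower bound being" 10% or less, with an expected CR rate of at least 25%. Section 10.1 counts patients who start therapy but miss the primary evaluation as not in CR, which can only lower the CR count. Section 10.1 also leaves room for additional exploratory analyses.

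**The concern.** When all responders, or none, fall in one category of a factor, the likelihood of an ordinary logistic model rises without limit as the coefficient grows. The fitted odds ratio is then infinite, or whatever large number the software stopped at. The standard error explodes, and a Wald test returns a p-value near 1 however strong the pattern in the data.

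With about 5 responders in 20, this is an ordinary event for an uncommon binary factor or for a genotype fitted as separate categories. Germline SNPs are a stated exploratory objective, and uncommon categories are most plausible there. At stake is whether some of the planned biomarker results can be estimated and reported at all by the named method. Barring multivariable models does not help, because the problem arises with a single covariate.

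**Working it through.** **Inputs.** N = 20, expected CR rate 25%, rate to exclude 10%, one-sided 90% Agresti-Coull bound (section 10.8). Logistic and Cox models with one covariate (section 10.7.1). Carrier counts, prevalences and allele frequencies are assumptions; the documents give none.

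**1. The plan's own figure.** With z = 1.2816 and z² = 1.642, the adjusted size is 21.642.
- 4/20: adjusted rate (4 + 0.821)/21.642 = 0.2228; lower bound 0.2228 − 1.2816 × √(0.2228 × 0.7772/21.642) = 0.108.
- 3/20: the same formula gives 0.0715.

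At least 4 CRs are therefore needed. P(4 or more | 20, 0.25) = 0.775, against the stated 0.80. The gap does not affect this point. What matters is the expected count, 20 × 0.25 = 5. At exactly 25%, P(5 or fewer) = 0.62.

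**2. Chance of an empty cell with exactly 5 CRs and no association** (hypergeometric).
- 4 carriers: no CR among carriers, C(15,4)/C(20,4) = 1365/4845 = 0.2817; all four carriers in CR, 5/4845 = 0.0010. Total 28%.
- 6 carriers: 5005/38760 = 0.1291, plus all CRs among carriers, 15/38760 = 0.0004. Total 13%.
- 10 carriers: 2 × 3003/184756 = 3%.
- Continuous factor without ties: 2/C(20,5) = 2/15504 = 0.01%.

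**3. Letting the CR count vary, true rate 25%, no association.**
- Binary factor: 39% at prevalence 0.2, 23% at 0.3, 14% at 0.5.
- Three-level genotype fitted as categories (simulated, minor-allele frequency 0.1 to 0.5): 53% to 66%.
- Genotype coded additively: 3% to 41%, highest for the rarest allele.

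**4. Chance of an empty cell with a strong association.** Assume two groups of 10 with true CR rates of 45% and 5% (average 25%). P(no CR in the low group) = 0.95^10 = 0.599. The other empty cells add little (0.55^10 = 0.003), so the total is about 60%.

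**5. What the methods report for 5/10 against 0/10.**
- Ordinary logistic, Wald: the coefficient diverges; p about 1.
- Likelihood ratio: 2 × [10 ln 0.5 − (5 ln 0.25 + 15 ln 0.75)] = 8.63 on 1 df, p = 0.003. The odds ratio is still infinite.
- Fisher: 2 × C(10,5)/C(20,5) = 504/15504 = 0.033.
- Firth (0.5 added to each cell): OR = (5.5 × 10.5)/(5.5 × 0.5) = 21. The log-OR standard error is √(1/5.5 + 1/5.5 + 1/0.5 + 1/10.5) = 1.57, giving a 95% Wald interval of 0.97 to 454. Profiling the penalised log-likelihood (log-likelihood plus half the log determinant of the information) to a drop of 3.84/2 gives about 1.8 to 2,960.

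The Wald interval covers 1 and the profile interval does not, so the type of interval has to be named as well as the method.

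**6. Cox.** Section 1.1.4 cites durable remissions beyond one year in 10% to 15% of patients on two intravesical agents. If dovitinib did no better, about 17 to 18 of 20 would relapse. Simulation with 15 to 18 relapses (exponential times, no association) gives a monotone likelihood in 1% to 3% of trials at prevalence 0.2, at most 0.01% at 0.5, and 6% to 12% at 0.1.

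**7. Cost of Fisher.** With 5 CRs, the true size of a nominal 5% test is 3.2% with 4 carriers (tables with 3 or 4 CRs among carriers), 1.4% with 6 and 3.3% with 10.

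**The case against.** The strongest reply is that the null percentages in step 2 describe sparse tables with nothing in them. With 4 or 6 carriers, nearly all the probability is zero CRs among a few carriers, where Fisher gives p = 0.53 and p = 0.26. A better method would find no signal there either. This stands: those figures show how often the estimate fails, not how often a lead is lost. A reader might infer that the biomarker questions will be answered wrongly wherever they matter most. The documents do not support that. Section 10.7.1 does not commit to a Wald test, and a diverging estimate is visible to any analyst. Section 10.1 allows further exploratory analysis. The case for change rests on step 4, which uses assumed effects, and on the lack of a named remedy.

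It is also fair to say that the plan expects 5 or more CRs, not fewer, and that balanced factors, age and most of the Cox work are little affected.

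A second tempting inference concerns section 10.7.1's statement that "Pre- and post-treatment phosphorylation changes in FGFR and VEGFR pathways will be analyzed by paired t-tests". Section 7.10.6.2 says "Staining intensity will be graded 0, +1, +2, +3", so one might conclude that t-tests are being run on a four-level ordinal score. That grading is for FGFR3 over-expression at study entry. Section 7.10.6.6, which governs the pathway markers, states no scale. Even on a 0 to 3 score, simulated type I error was 0.044 to 0.052 with 15 to 20 pairs for uniform or moderately skewed scores, and mostly below 5% otherwise. The t-test is not shown to be an error.

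**Conclusion.** The point holds for associations between 6-month CR and categorical factors that are uncommon or fitted as several categories. There, ordinary logistic regression will often have no finite estimate, and the plan does not say what happens then. The exact frequency depends on carrier counts and genotype coding that the documents do not give; across the binary cases with exactly 5 CRs it runs from 3% (10 of 20) to 28% (4 of 20). Under a strong, assumed effect in balanced groups it is about 60%.

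The consequence is limited. The analyses are hypothesis generating and the primary estimate is untouched. This is an optional improvement, worth making because it costs almost nothing.

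**What to change.** In section 10.7.1, for categorical factors against 6-month CR, replace ordinary logistic regression with Firth-penalised logistic regression and penalised-likelihood intervals, or with exact logistic regression and exact intervals. Report Fisher's exact p for 2x2 tables. State how genotypes will be coded. Keep ordinary logistic regression for continuous factors. Keep ordinary Cox regression for RFS, moving to Firth Cox only if the likelihood is monotone.

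As a side note, state the scoring scale for the pathway markers in section 7.10.6.6. If it is ordinal, an exact sign or signed-rank test would suit it.

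The cost is wording and slightly more analysis work, with no new data, patients or visits. The real downside is conservatism: Fisher's true size here is about 1% to 3%, so some modest associations will be missed. Exact intervals will also have one infinite end when a cell is empty, which favours the Firth interval for display.
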